8.1.8. Exploratory Assessments of Hand Eczema

8.1.8.1. History, Subtype, Clinical Signs, and Extent

Participants will undergo evaluation at the screening visit of the presence and chronicity of hand eczema.⁴⁶ Not all participants are expected to have hand eczema. For participants with bilateral hand eczema, the Investigator will identify the worse hand, which will be the target hand for evaluation throughout the study. Participants with hand eczema will also undergo assessments of the subtype(s) (at sites that have capacity for this), clinical signs, and extent of hand eczema.^{46, 47, 48, 49, 50} They will also be examined to determine if they have eczema of the feet.⁴⁷

8.1.8.2. Investigator's Global Assessment (IGA) of Hand Eczema

The Investigator's Global Assessment of hand eczema is scored on a 5-point scale (0-4), reflecting a global consideration of erythema, scaling, and fissuring/cracking of the target hand, selected at the screening visit.⁵¹ The clinical evaluator of hand eczema will perform an assessment of the overall severity of hand eczema of the target hand and assign an IGA score and category as described in Table 6. The assessment will be a static evaluation without regard to the score at a previous visit.

Table 6. Investigator's Global Assessment (IGA) of Hand Eczema Score

Score	Category	Description^a
0	Clear	No signs of hand eczema.
1	Almost Clear	Just perceptible scaling and/or erythema.
2	Mild	Mild scaling, and/or mild erythema and/or mild cracking.
3	Moderate	Moderate scaling, and/or moderate erythema and/or moderate cracking/ fissuring.
4	Severe	Severe scaling, and/or severe erythema and/or severe cracking/fissuring.

a. If the participant has bilateral hand eczema, the worse hand is assessed.

8.2. Safety Assessments

Planned time points for all safety assessments are provided in the [SoA](#).

8.2.1. Medical History and Physical Examinations

- Complete AD disease history includes collection of details of AD at Screening: AD diagnosis, the use of topical treatments, systemic treatments and other treatments for AD. Medical history in addition to AD history including disease duration will be collected at screening. Medical history also includes history of alcohol, and tobacco use. Smoking status and average weekly alcohol consumption (units/week) will be collected, where a unit contains 12 g of pure alcohol, an amount equivalent to that contained in 5 oz/150 mL (a glass) of wine, 12 oz/360 mL of beer, or 1.5 oz/45 mL of 90 proof of spirits. Additionally, a record of prior vaccinations will be obtained to determine if the participant has received tetanus, diphtheria and/or pertussis vaccines within the past 5 years.
- Complete medication history of all prescription or nonprescription drugs, and dietary and herbal supplements taken within 28 days prior to the planned first dose, except as noted below:

The following timeframe prior to the planned first dose must be used for collection of the following Current/Prior Medications:

- 1 year: Previous non-systemic drug treatments for AD including topical treatments;
- Lifetime history of previous systemic treatment for AD and reason for stopping any systemic treatment for AD;
- Lifetime history of intolerance/allergy to any drug, regardless of indication.
- Complete physical examinations must be performed by the investigator, sub-investigator or a qualified health professional per local guidelines. Complete physical examinations consist of assessments of general appearance; skin; head, eyes, ears, nose and throat (HEENT); mouth; heart; lungs; breast (optional); abdomen; external genitalia (optional); extremities; neurologic function; and lymph nodes. In addition, height (screening visit only) and weight (screening, Week 0, Week 12, and Week 20 visits) will also be recorded.
- Targeted physical examinations must be performed by the investigator, sub-investigator or a qualified health professional per local guidelines and should include skin, heart, lungs, and abdomen and examination of body systems where there are symptom complaints by the participant.
- Investigators should pay special attention to clinical signs related to previous serious illnesses.

- All AEs regarding conjunctivitis should be referred for an ophthalmology exam.
- All AEs regarding conjunctivitis, herpes zoster, and acne or folliculitis should have additional details collected.

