8. STUDY ASSESSMENTS AND PROCEDURES

Every effort should be made to ensure that protocol required tests and procedures are completed as described. However, it is anticipated that from time to time there may be circumstances outside the control of the investigator that may make it unfeasible to perform the test. In these cases, the investigator must take all steps necessary to ensure the safety and wellbeing of the participant. Guidance on the conduct of study procedures in the context of COVID-19 or other virus/infection or public health related travel restrictions or emergency is described Appendix 10.13. When a protocol required test cannot be performed, the investigator will document the reason for the missed test and any corrective and preventive actions that he or she has taken to ensure that required processes are adhered to as soon as possible. The study team must be informed of these incidents in a timely manner.

- Study procedures and their timing are summarized in the [SoA](#). Protocol waivers or exemptions are not allowed.
- Immediate safety concerns should be discussed with the sponsor immediately upon occurrence or awareness to determine if the participant should continue or discontinue study intervention.
- Adherence to the study design requirements, including those specified in the [SoA](#), is essential and required for study conduct.
- All screening evaluations must be completed and reviewed to confirm that potential participants meet all eligibility criteria. The investigator will maintain a screening log to record details of all participants screened and to confirm eligibility or record reasons for screening failure, as applicable. Participants will be screened (Visit 1) within approximately 28 days prior to administration of the study intervention to confirm that they meet the participant selection criteria for the study. Use of screening procedures exceeding 28 days prior to randomization should be discussed with the Pfizer medical monitor. The investigator (or an appropriate delegate at the investigator site) will obtain informed consent from each participant, in accordance with the procedures described in [Section 10.1.3](#) of [Appendix 1](#).

- If the Mantoux PPD tuberculin skin test is given, the participant must return between 48-72 hours post-injection for induration evaluation.

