3.5. Baseline Variables

In general, for all analyses, baseline will be defined based on observations collected prior to first dose if dosing time is available. For DLQI, EQ-5D-5L, HADS and POEM, baseline will be defined based on observations collected on or prior to the day of first dose. Baseline values for demographics, medical and other history, atopic dermatitis history will be based on measures collected at Visit 1/Screening visit. Study Day 1 is defined as the day the participant receives first dose of study drug. For purposes of all other analyses including analyses for change from baseline, the baseline value will be defined as measured on Day 1. If a value is missing on Day 1, then the last available observation before Day 1 will be used.

For all analyses described in Section 5.2 where baseline disease severity (IGA = moderate vs severe) is used as a stratum or covariate, if a subject is erroneously enrolled with baseline IGA = mild, they will be considered as moderate IGA in the strata or covariate.

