3.6.3. Vital Signs, including Height and Weight

Vital sign measurements are oral or tympanic temperature, respiratory rate, pulse rate, and blood pressures.

Height is collected at screening and weight is collected at Screening, Baseline, Week 12 and Week 20 visits.

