6.6. Safety Summaries and Analyses

Safety analysis will be based on the SAF analysis set.

All clinical AEs, SAEs, treatment-emergent signs and symptoms (TEAEs), withdrawal due to AEs, ECGs, vital signs and safety laboratory data will be reviewed and summarized on an ongoing basis during the study to evaluate the safety of participants.

Safety data will be presented in tabular and/or graphical format and summarized descriptively, where appropriate. All safety endpoints will be listed and summarized in accordance with CaPS. Categorical outcomes (eg, AEs) will be summarized by participant counts and percentage. Continuous outcome (eg, blood pressure, pulse rate, etc.) will be summarized using N, mean, median, standard deviation, etc. Change from baseline in laboratory data, ECGs, physical exams and vital signs will also be summarized. Participant listings will be produced for these safety endpoints accordingly.

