6.6.3. Vital Signs

Vital signs will be summarized at Baseline and at Weeks 2, 4, 8, 12, 16, 20 and 26. Height will be reported at baseline only and weight will be summarized at baseline, Week 12 and Week 20.

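### The weight and height rows of the Schedule of Activities are transposed, so the grid omits the weights planned at Weeks 0, 12 and 20

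*Protocol*

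**What the plan says.** Three statements in the running text agree on when height and weight are taken or reported:

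- Protocol Section 8.2.1: "height (screening visit only) and weight (screening, Week 0, Week 12, and Week 20 visits) will also be recorded".
- SAP Section 3.6.3: "Height is collected at screening and weight is collected at Screening, Baseline, Week 12 and Week 20 visits".
- SAP Section 6.6.3: height is reported at baseline only, and "weight will be summarized at baseline, Week 12 and Week 20".

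The Schedule of Activities (SoA, Protocol Section 1.3) differs. Its weight row carries a single mark, at screening. Its height row carries four, at screening, Day 1, Week 12 and Week 20. Both rows refer the reader to Section 8.2.1.

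Two statements give the grid operative force. Section 8.2 begins "Planned time points for all safety assessments are provided in the" SoA. Section 8 has a bullet that starts "Adherence to the study design requirements, including those specified in the" SoA, and it treats that adherence as mandatory.

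**The concern.** The protocol gives two incompatible schedules for the same measurements, and it hands the timing of safety assessments to the one that looks wrong. Participants are adults, so four heights and one weight over 26 weeks is not a plausible intention.

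A site that uses the grid as its visit checklist would not weigh participants at Weeks 0, 12 and 20, and would measure height three times more than intended. A site that follows Section 8.2.1 would depart from the SoA. On-treatment weights that are not taken at the visit cannot be collected afterwards.

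**Working it through.** There is no power or error-rate figure to reproduce. The check is a comparison of visit lists followed by a count.

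**Step 1: read the SoA rows.** The visit columns are, in order, Screening, Week 0 (Day 1), Weeks 1, 2, 4, 8, 12, 16, 20, 24, 26 and 30, followed by Notes. That makes 13 cells after the row label. The vital signs, weight, height and chest X-ray rows each have exactly 13 cells.

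| Source | Weight | Height |
|---|---|---|
| SoA, Section 1.3 | Screening | Screening, Weeks 0, 12, 20 |
| Protocol 8.2.1 | Screening, Weeks 0, 12, 20 | Screening |
| SAP 3.6.3 | Screening, Baseline, Weeks 12, 20 | Screening |
| SAP 6.6.3 (reporting) | Baseline, Weeks 12, 20 | Baseline |

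The SoA is an exact exchange of the two lists. Swapping its two rows reproduces Section 8.2.1 and SAP 3.6.3 and supplies every weight visit that SAP 6.6.3 needs.

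**Step 2: test whether the table reads reliably.** Other rows were compared with schedules stated elsewhere:

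- Vital signs are marked at Screening and Weeks 0, 2, 4, 8, 12, 16, 20, 26 and 30. This covers every visit in SAP 6.6.3 (baseline and Weeks 2, 4, 8, 12, 16, 20, 26).
- HBV DNA is marked at Screening, Week 16 and Week 26, as in Protocol Section 8.2.5.1.
- DLQI after baseline and up to end of treatment is marked at Weeks 2, 12, 16, 20 and 26, as in SAP Section 6.2.2.2.

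Labels and marks agree in each of these rows.

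**Step 3: count the measurements at stake**, with 600 planned participants, before dropout:

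- Weights under Section 8.2.1: 4 × 600 = 2400.
- Weights on the SoA: 1 × 600 = 600.
- Planned weights absent from the SoA: 2400 − 600 = 1800, of which 2 × 600 = 1200 fall at Weeks 12 and 20.

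**Step 4: separate what can be recovered.** SAP Section 3.5 states: "If a value is missing on Day 1, then the last available observation before Day 1 will be used". The screening weight therefore serves as baseline, both for the summary and for the weight subgroups in SAP Section 6.4. No such rule covers Weeks 12 and 20.

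**Step 5: give a range.** The documents do not say how many participants are at sites that would follow the grid row. The shares below are assumptions.

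| Assumed share | Weights missing at each of Weeks 12 and 20 |
|---|---|
| 10% | 0.10 × 600 = 60 |
| 25% | 0.25 × 600 = 150 |
| 50% | 0.50 × 600 = 300 |
| 100% | 1.00 × 600 = 600 |

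**The case against.** The strongest objection is that the table may have been damaged in text extraction. Some header labels in this SoA are visibly displaced. The cell count and the vital signs comparison test column alignment, whereas the risk is an exchange of two adjacent row labels. The weight and height rows carry the same note, so nothing inside either row ties its label to its marks. This stands as a reason to look at the source PDF. It does not outweigh the rest: extraction would have had to exchange only these two labels and leave the neighbouring rows intact.

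Second, both rows send the reader to Section 8.2.1, which has the right schedule. That lowers the chance of lost data. It does not remove the conflict, because Section 8.2 sends the reader back to the SoA for timing.

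Third, the consequence is small. Dosing is fixed, and no efficacy analysis or discontinuation criterion uses on-treatment weight. Nor is a change from baseline in weight explicitly planned. SAP Section 6.6 says "Change from baseline in laboratory data, ECGs, physical exams and vital signs will also be summarized", but the measurements that SAP 3.6.3 lists as vital signs do not include weight, although its heading does. This is right, and it confines the certain loss to the descriptive weight summaries at two visits.

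Fourth, the participant counts rest on assumed shares, and the 100% case requires every site to ignore the cross-reference. That is also right. The range shows scale and is not a forecast.

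**Conclusion.** The concern holds as a minor error in the SoA. On the text as supplied, the grid schedules one weight and four heights where Section 8.2.1 and the SAP intend four weights and one height. Three of the four planned weights are therefore off the grid, and two of those three, at Weeks 12 and 20, have no fallback.

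The effect is limited to incomplete descriptive weight summaries at those visits and, if weight is treated as a vital sign, to its change from baseline. Baseline weight, the weight subgroup, the efficacy analyses and the stopping rules are unaffected. Confidence is medium. The conclusion assumes that the row labels were read correctly from the PDF, and the number of missing values depends on site behaviour that the documents do not describe.

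**What to change.** Confirm the two row labels against the source PDF. If they read as above, exchange the rows in Section 1.3, so that weight is marked at screening, Week 0 (Day 1), Week 12 and Week 20, and height at screening only. Send sites a clarification letter at once, since missed on-treatment weights cannot be collected later.

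Section 8.2.1 and the SAP need no change. The cost is one table correction and one letter. The correction adds no procedure beyond Section 8.2.1 and takes three height measurements per participant off the SoA.

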8.2.2. Vital Signs

- Temperature (oral or tympanic), pulse rate, respiratory rate, and blood pressure will be assessed (pre-dose, if applicable).
- Blood pressure and pulse measurements will be assessed with the participant in a seated position, after at least 5 minutes of rest in a quiet setting without distractions, using a standard calibrated blood pressure measuring device. A blood pressure device that uses multiple cuff sizes based on the arm circumference is the required type of device. The appropriate cuff size for the participant must be used to ensure accurate measurement. The arm circumference at the midpoint of the length of the upper arm should be measured to determine the appropriate cuff size in accordance with the specifications of the BP measuring device. The same properly sized and calibrated blood pressure cuff will be used to measure blood pressure each time. Participants should be seated in a chair, back supported, and arms bared (free of restrictions such as rolled up sleeves, etc.) and supported at heart level. Measurements should be taken on the same arm at each visit (preferably non-dominant). Participants should refrain from smoking or ingesting caffeine during the 30 minutes preceding the measurements.
- Vital signs will be measured in a seated position after 5 minutes rest and will include temperature, systolic and diastolic blood pressure, and pulse. Heart rate should be measured at approximately the same time as BP for a minimum of 30 seconds. When the timing of BP and pulse (heart) rate measurements coincides with a blood collection or other study procedure, BP and pulse (heart) rate should be obtained first.

8.2.3. Chest X-Ray

Chest X-ray or other appropriate diagnostic image (ie, computerized tomography or magnetic resonance imaging) to aid in TB status determination may be performed up to 12 weeks prior to Day 1. Chest X-rays (posterior/anterior and lateral views) are required. Official reading must be located and available in the source documentation.

8.2.4. Electrocardiograms

- A single 12-lead ECG will be performed at visits specified in the [Schedule of Activities](#) after the participant has rested for at least 10 minutes quietly in the supine position. ECG will be interpreted by a central reader. Clinically significant or exclusionary ECG findings at the screening visit will result in screen failure.

- A participant's screening ECG must not demonstrate clinically significant abnormalities prior to randomization.
- If a post-dose corrected Q wave interval (QTc) interval remains ≥ 30 msec from the baseline and is >450 msec; or b) an absolute QTc value is ≥ 500 msec for any scheduled ECG for greater than 4 hours (or sooner, at the discretion of the investigator), or QTc intervals get progressively longer, the participant should undergo continuous ECG monitoring. A cardiologist should be consulted if QTc intervals do not return to less than the criterion listed above after 8 hours of monitoring (or sooner, at the discretion of the investigator).
- In some cases, it may be appropriate to repeat abnormal ECGs to rule out improper lead placement as contributing to the ECG abnormality. It is important that leads be placed in the same positions each time in order to achieve precise ECG recordings. If a machine read QTc value is prolonged, as defined above, repeat measurements may not be necessary if a qualified medical provider's interpretation determines that the QTc values are in the acceptable range.
- ECG values of potential clinical concern are listed in [Appendix 8](#).

8.2.5. Clinical Safety Laboratory Assessments

- See [Appendix 2](#) for the list of clinical laboratory tests to be performed and to the [SoA](#) for the timing and frequency. Refer to [Appendix 11](#) for monitoring and discontinuation criteria.
- Participants must abstain from all food and drink (except water and non-study medications) for an 8-hour overnight fast prior to labs that include the lipid profile panel as per the Schedule of Activities. All other labs do not require fasting.
- Sample collection, labeling, storage, and shipping information can be found in the laboratory manual.
- The investigator must review the laboratory report, document this review, and record any clinically relevant changes occurring during the study in the AE section of the CRF. The laboratory reports must be filed with the source documents. Clinically significant abnormal laboratory findings are those which are not associated with the underlying disease, unless judged by the investigator to be more severe than expected for the participant's condition.
- All laboratory tests with values considered clinically significantly abnormal during participation in the study or within 28 days after the last dose of study intervention

should be repeated until the values return to normal or baseline or are no longer considered clinically significant by the investigator or medical monitor.

- If such values do not return to normal/baseline within a period of time judged reasonable by the investigator, the etiology should be identified and the sponsor notified.
- All protocol-required laboratory assessments, as defined in Appendix 2, must be conducted in accordance with the laboratory manual and the SoA.
- If laboratory values from non-protocol specified laboratory assessments performed at the institution's local laboratory require a change in participant management or are considered clinically significant by the investigator (eg, SAE or AE or dose modification), then the results must be recorded in the CRF.

8.2.5.1. Hepatitis Testing

Hepatitis B (HB) testing: HB surface antigen (HBsAg), HB core antibody (HBcAb), HB surface antibody (HBsAb), HBV DNA (where required).

- Participants who are HBsAg negative, HBcAb positive, and HBsAb positive at Screening will have reflex testing for HBV DNA. Participants who have HBV DNA above the LLQ are excluded. Participants who have HBV DNA negative or below LLQ may be randomized but will have HBV DNA testing repeated at Week 16 and Week 26 End of Treatment (EOT) visit, or Early Discontinuation (ED) visit, whichever is sooner (refer to [Section 7.1.](#)). A single HBV DNA test result above the LLQ for a participant requires immediate and permanent discontinuation from treatment.

Interpretation of Hepatitis B Testing Results:

HBsAg negative and HBcAb negative: Participant is eligible for the study;

HBsAg positive and HBcAb negative: Participant is excluded from study participation;

HBsAg negative and HBcAb positive and HBsAb positive: Participant may be eligible for study if HBV DNA is negative or below LLQ;

HBsAg negative and HBcAb positive and HBsAb negative: Participant is excluded from study participation.

Hepatitis C testing: Hepatitis C virus Antibody (HCV Ab), Hepatitis C virus ribonucleic acid (RNA) (HCV RNA for confirmation of positive HCV Ab result).

Interpretation of Hepatitis C Testing Results:

HCV Ab positive and HCV RNA positive: Participant is excluded from study participation.

8.2.5.2. Tuberculosis Testing

A documented TB test performed within 12 weeks prior to Day 1 (Week 0) is acceptable.

- Perform TB test procedure using the QuantiFERON®-TB Gold In-Tube Test (QFT-G). The QFT-G may be repeated once if the investigator deems this to be necessary.
- A Purified Protein Derivative (PPD) test may be performed if the central laboratory is unable to determine results of QFT-G. Should the PPD test be required, the test must be administered and evaluated by a health care professional 48 to 72 hours later, unless performed and documented within the last 3 months. The test should be performed according to local standards with induration of <5 mm required for inclusion.
- Other TB testing may be performed at a local lab with approval from the Pfizer clinician.

Participants with a history of tuberculosis may not require TB testing as per the protocol exclusion criteria in [Section 5.2](#).

In addition to protocol required TB testing, a chest X-ray (or other imaging as specified in [Section 8.2.3](#)) is required, unless previously performed and documented within 12 weeks prior to Study Day 1. Refer to [Section 8.2.3](#).

